7.6 Medication/Supplement Log

A patient medication log will be kept and administered to track the usage and dose of support medications as well as dietary supplements including herbal medicine. Support medications include, but are not limited to: (1) Anti-depressants including selective serotonin reuptake inhibitors (SSRIs) and serotonin-norepinephrine reuptake inhibitors (SNRIs): Citalopram (Celexa), Escitalopram (Lexapro), Fluoxetine (Prozac), Fluvoxamine (Luvox), Paroxetine

(Brisdelle, Paxil), Sertraline (Zoloft), Venlafaxine (Effexor), and Desvenlafaxine (Pristiq); (2) Antiseizure medications: Gabapentin; (3) Dietary supplements include, but are not limited to: Vitamin E, Black cohosh, Dong quai root, Evening primrose oil, Flaxseed, Ginseng root, Omega-3 fatty acid, Red clover extract, and Soy supplements; (4) Sleep medications; (5)Mixtures of multi-herbal formulas (Traditional Chinese Medicine, TCM), either in a patient pill form or in a personalized tea/liquid form. Data for the medication log will be collected at each scheduled visit.

7.7 Acupuncture Expectancy Scale (AES)

The AES consists of four items measuring the expectation of improvement of illness (symptom), enhanced coping, increased vitality, and symptom alleviation due to acupuncture therapy. Participants are asked to endorse their expectancy of acupuncture for specific symptoms (e.g., joint pain for breast cancer survivors, and fatigue for patients undergoing radiation therapy). Subjects are asked to rate from 1 to 5 on a five-point Likert scale, with 1 indicating “Not at all agree” and 5 indicating “Completely agree” with the expected improvement as result of acupuncture. Possible scores range from 4 to 20, with higher scores indicating greater expectancy. Preliminary validation showed that the AES has a single factor structure with an acceptable reliability coefficient. Additionally, the score on the AES was positively correlated with both the perceived effectiveness of acupuncture treatment and the confidence in acupuncture care. The AES will be administered once before the randomization process.^{59, 60}

7.8 Acupuncture Treatment Form (ATF)

An acupuncture treatment form will be generated by the treating acupuncturist at each acupuncture treatment. The form will document the following items: acupuncture points used, patient-reported acupuncture intensity, patient immediate responses, and any acupuncture-related adverse events.

7.9 NF-Kb, STAT-1 and STAT-3, and associated cytokines IL-8, TNF-alpha and IL-6, and T-cells Measurement

Venous blood will be collected at baseline and at week 10. Assays will be performed at the Harvard Catalyst Central Laboratory (HCCL) and [name] Lab at Dana-Farber Cancer Institute. Briefly, for each sample, 10 mL of venous blood will be collected into EDTA and Serum tubes.. Samples will be centrifuged for 15 minutes at 1000 x g within 30 minutes of collection and then aliquot and stored at -80 °C for future measurements.

The plasma levels of interferon gamma (IFN γ), tumor necrosis factor- α (TNF- α), interleukin-1 β (IL-1 β), IL-6, IL-8, and IL-17A will be determined using a Millipore cytokine seven-plex panel assay (MILLIPLEX MAP Human Cytokine/Chemokine Magnetic Bead Panel) (Milliplex MAP kits, EMD Millipore, Billerica, MA, USA). The plasma levels of interferon-inducible protein-10 (IP10), monocyte chemoattractant protein-1 (MCP-1), and macrophage inflammatory protein-1 β (MIP-1 β) will be measured using a Millipore cytokine three-plex panel assay (MILLIPLEX MAP Human Cytokine/Chemokine Magnetic Bead Panel) (Milliplex MAP kits, EMD Millipore, Billerica, MA, USA). These assays will be processed according to the

manufacturer's instructions. STAT-1, STAT-3 and NF-κB expression levels will be measured at [name] Lab. Samples will be measured in duplicate, and the average of the 2 values will be used in the statistical analysis.

7.10 Sleep Diary

Weekly sleep diary will be collected at three time points: baseline, week 10, and week 20. Participants will be instructed to complete the diary upon awakening to minimize recall bias. The format of the sleep diary and wording of the questions have been modeled after the Consensus Sleep Diary, a standardized and validated tool for collecting subjective sleep patterns.^{63,64} Using the diary, participants will keep track of their time to bed with intention of sleeping, amount of time it took to fall asleep, number and total duration of awakenings, final awakening time, number and duration of napping, and number of hot flashes interfering with sleep. This information will then be used to assess various sleep-related parameters, such as sleep onset latency, wake after sleep onset, number of nightly awakenings, total sleep time, and sleep efficiency.

7.11 Insomnia Severity Index

Insomnia Severity Index (ISI) is a widely used, validated patient-reported questionnaire for assessing insomnia severity.⁶⁵ It is composed of 7 questions, each scored on a 5-point scale (range 0-4) and the total scores ranging from 0 to 28. Higher scores correspond to a more severe insomnia and an 8-point reduction are considered clinically meaningful. The ISI will be collected at three time points: baseline, at week 10, and week 20.

8. STUDY INTERVENTIONS

8.1 Overview

It is expected that each patient who is assigned to the immediate acupuncture arm will receive acupuncture twice per week for 10 weeks for a total of 20 sessions. The participants on the usual care/wait list control arm will continue their standard usual care with their physicians and care team. The crossover will take place after the 10th week. After crossover, the participants initially on the usual care/waiting list arm will receive the identical acupuncture protocol but a less frequent schedule from week 11 to week 20: once per week for a total of 10 sessions. The participants who were initially treated with acupuncture will enter a follow-up phase of usual care for 10 weeks from week 11 to week 20.

8.2 Usual Care

Usual care in the current study is defined as the current standard of care with non-hormonal pharmacotherapy of western medicine.⁴⁶ Participants should not receive acupuncture or acupuncture-like therapy during the usual care portion of study follow-up.

8.3 Acupuncture

The acupuncture protocol outlined below is based on the best evidence available in this specialty. The following data is collected: 1) an English- and Chinese-language literature review of previous clinical studies of acupuncture used for hot flashes;^{3, 61} 2) English- and Chinese-language acupuncture text books that describe treatment strategies for hot flashes;⁶² and 3) our own clinical experience with breast cancer patients treated at the Leonard P. Zakim Center for Integrative Therapies and Healthy Living at DFCI.

Treatments will be administered by experienced, licensed and credentialed DFCI oncology acupuncturists who have been specifically trained to administer this study's acupuncture protocol. To facilitate study recruitment and to reduce traveling time, participants will be offered the option to receive treatments at the Zakim Center clinic or at the private clinics of the study acupuncturists in the Greater Boston Area. Participants will be provided with a list of the private clinic locations (see Appendix XII) and will communicate their preferences for treatment location to study staff at the time of consent.

Private Clinic Details

The locations and operating hours of the private clinics are:

- 1) **Name:** [name]
Location: [name]
[contact]
Available Time: Thursday 9am-5:00pm, Saturday 9 am to 5 pm
- 2) **Name:** [name]
Location: [name]
[contact]
Available Time: Tuesday 8 am -5pm, Thursday 8 am- 5pm, Saturday by appointment

- 3) **Name:** [name]
Location: [name]
[contact]
Available Time: Monday-Saturday 10 am to 5 pm, except on Tuesdays
- 4) **Name:** [name]
Location: [name]
[contact]
Available Time: Monday, Tuesday, Friday 8 am to 6 pm; Thursday 12 noon-6pm

At these private clinics, the acupuncture treatment will be provided by the study-trained DFCI staff acupuncturists listed above. These acupuncturists are also responsible for administering the study protocol in the Zakim Center. Participants that opt for off-site treatment will be asked to remain at the same site with the same acupuncturist throughout their study treatment course. All study acupuncturists are licensed acupuncturists and have obtained certificates from CITI program for research ethics and human subject protection as required by DFCI, and in-person training with the study protocol.

If a study patient misses an acupuncture treatment, the patient will be asked to make up the missed treatment session so that a total of 20 sessions (or 10 sessions after crossover) of acupuncture will be provided. We will determine that a participant is compliant with the acupuncture protocol if the study participants complete overall at least 15 out of 20 planned sessions (75%) during the main treatment period. The total number of acupuncture sessions received will be recorded for each participant. Any side effects related to the acupuncture will be collected by treating acupuncturists.

Figure 2 and Table 2 present the names and locations of acupuncture points. (Figure 2, Table 2.).

Figure 2. Acupuncture protocol for hot flashes in breast cancer

During the main study period, acupuncture will be administered twice per week for ten weeks, for a total of 20 sessions. In the post-crossover period for the usual care (control) group, acupuncture will be administered once per week for ten weeks, for a total of 10 sessions.

The acupuncture protocol will use a two-phase, step-up protocol to gradually increase the treatment area and treatment intensity. Based on our experience at the Zakim Center, this protocol will reduce the initial anxiety of participants to the treatment and maximize the treatment intensity. The phase 1 treatment will take place at the first visit, in which only manual acupuncture will be employed. The phase 2 treatment will take place from the second to twentieth visit, in which an electroacupuncture stimulation will be added. Use of electroacupuncture is a typical practice at Zakim Center. In post-crossover acupuncture, phase 1 will be the first visit and the phase 2 will start at the 2nd visit and extend to the 10th visit.

At each visit, participants will be asked to lie down in a supine position on a massage table with

the arms, legs and abdomen exposed to the treatment. The skin on the acupuncture points will be prepared with 70% ethyl alcohol. Then, acupuncture needles (0.20x25 mm, and 0.25x 40 mm) will be inserted into acupuncture points bilaterally. The depth of insertions at each point will be between 5-15 mm, except on points on the head and ears, which will be between 2-5 mm. Depth of needling to access acupuncture channels will vary due to differences in patient size and body characteristics. After insertion, acupuncture needles will be manually manipulated in order to obtain the De Qi sensation. The De Qi sensation is defined as the acupuncturist feeling a tugging or grasping sensation from the needle manipulation and the patient feeling soreness, fullness, heaviness or local distension at local needling sites. The De Qi sensation will be required on at least 2 points bilaterally on the lower extremity and at least 1 point bilaterally on the upper extremity. During phase 2 of the treatment protocol, and after De Qi is obtained, electroacupuncture will be administered to a subset of acupuncture points. Six pairs of microalligator clips from the AWQ-104L electroacupuncture machine (Lhasa OMS, Inc.) will be connected with the needles at GV20 and Yintang on the head; Shenmen and Heart, on the ears bilaterally, with the negative poles on the Yintang/Heart and the positive poles on GV20/Shenmen. The stimulation parameters will be set at a 2/10 Hz alternating wave pattern, with a 40 or 350 μ s pulse-widths. The targeted stimulation intensity reported by the patient will be at 3 or 4 on the scale from 0 to 10 (0 being feeling nothing at all and 10 being the strongest one can imagine). The patient will be asked to report sensations and should feel comfortable with the intensity of the electrostimulation. The usage of an infrared heat lamp during the session, a common practice in an acupuncture session, maybe used on the feet of the patient. The needles will remain in place for 30 minutes. The patient will be left alone in the treatment room with dimmed lights. A call bell will be available to the study patient during the treatment period. After 30 minutes of treatment, needles will be manually manipulated again before removal. De Qi sensation is not required at this time. The patient will leave the treatment room after the treatment. A complete list of acupuncture points that will be used is listed in Table 2. A total of 19 needles will be used during each acupuncture session at each phase respectively. Additionally, the following rules are applied: a) the selections of LI11 and PC7 points will be determined based upon locations of symptoms reported by participants: if the participants had axillary lymph node dissection (ALND) or has lymphedema, the affected limb won't be needled; b) the electrostimulation may be omitted at Shenmen/ear and Heart/ear pending the tolerability of each participant; c) if the participant refuses electrostimulation, manual acupuncture may be performed without electrostimulation. The number of needles will be counted at the end of each session.

8.4 Adverse Events

Individuals receiving acupuncture will be asked about acupuncture-related adverse events at each acupuncture treatment. Any acupuncture-related injuries will be reported to study investigators. Any reported events will be evaluated for the likelihood that they occurred as a result of acupuncture (clearly related, likely related, maybe related, doubtfully related, or clearly NOT related). Participants will also be provided a phone number to contact study staff at DFCI to report potential acupuncture-related adverse events.

Table 2. Acupuncture Points and Locations

Name	Pinyin Name	Location	Innervations
LR3	Taichong	On the dorsum of the foot, in the depression distal to the junction of the first and second metatarsal bones.	The branch of the deep peroneal nerve.
ST36	Zusanli	3 cun below Dubi, one finger-breadth from the anterior crest of the tibia, in m. tibialis anterior.	Superficially, the lateral aural cutaneous nerve and the cutaneous branch of the saphenous nerve; deeper, the deep peroneal nerve.
SP6	Sanyinjiao	3 cun directly above the tip of the medial malleolus, on the posterior border of the medial aspect of the tibia.	Superficially, the medial crural cutaneous nerve; deeper, in the posterior aspect, the tibial nerve.
K3	Taixi	In the depression between the medial malleolus and tendo calcaneus, at the level with the tip of the medial malleolus.	The medial crural cutaneous nerve, on the course of the tibial nerve.
LI11	Quchi	When the elbow is flexed, the point is in the depression at the lateral end of the transverse cubital crease, midway between Chize and the lateral epicondyle of the humerus.	The posterior antebrachial cutaneous nerve; deeper, on the medial side, the radial nerve.
PC7	Daling	In the meddle of the transverse crease of the wrist, between the tendons of m. palmaris longus and m. flexor carpi radialis.	Deeper, the median nerve.
CV6	Qihai	On the anterior midline, 1.5 cun below the umbilicus.	The anterior cutaneous branch of the eleventh intercostal nerve.
Extra2	Yintang	Midway between the medial ends of the two eyebrows.	N/A
GV20	Baihui	On the midline of the head; 7 cun directly above posterior hairline; approximately on midpoint of line connecting apexes of two auricles.	The branch of the great occipital nerve.
Ear point 1	Shenmen	Superior and central to the tip of the triangular fossa, between the junction of the superior crus and inferior crus of antihelix. It is not at the tip of the triangular fossa, but slightly inward and slightly upward from where the triangular fossa descends from the superior crus toward deeper regions of the triangular fossa.	auricular branches of the vagus nerve (ABVN)
Ear point 2	Heart	deepest, most central area of the inferior concha	auricular branches of the vagus nerve (ABVN)
Cun: The CUN system is a proportional measurement system used in Chinese acupuncture.			

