9. ADVERSE EVENT REPORTING REQUIREMENTS

9.1 Definitions

9.1.1 Adverse Event (AE)

An adverse event (AE) is any undesirable sign, symptom or medical condition or experience that develops or worsens in severity after starting the first dose of study treatment or any procedure specified in the protocol, even if the event is not considered to be related to the study.

Abnormal laboratory values or diagnostic test results constitute adverse events only if they induce clinical signs or symptoms or require treatment or further diagnostic tests.

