9.1.3.3 Attribution

Attribution is the relationship between an adverse event or serious adverse event and the study treatment. Attribution will be assigned as follows:

- Definite – The AE is clearly related to the study treatment.

11/8/2019

- Probable – The AE is likely related to the study treatment.
- Possible – The AE may be related to the study treatment.
- Unlikely - The AE is doubtfully related to the study treatment.
- Unrelated - The AE is clearly NOT related to the study treatment.

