Appendix VI. Acupuncture Treatment Form

Name of patient: _____ Hospital ID# : _____ Date of Visit : _____ Number of Sessions: _____ out of 12/6

1. Please make “X” below to indicate the points used, *De Qi* sensation, and electro-stimulation used at today’s session:

Points	LR3	K3	SP6	ST36	CV6	HT7	LI11	GV20	Y.T.	S.M.	Heart	Note
L												
R												
DeQi												
e-stim												

2. Please record on the line below regarding the electroacupuncture parameters used at today’s session:

Frequency: _____ Hz; Pulse width: _____ (40/350)µS; Pulse mode: _____ (DD/Conti.)

3. Please ask the study patient when you have just completed the adjustment of during the treatment session today and make a “X” below: “Please tell me, on a scale from 0 to 10, the intensity of the needling sensation you are experiencing right now; 0 is that you do not feel anything at all and 10 is the strongest sensation you could imagine.”

Intensity Score	0	1	2	3	4	5	6	7	8	9	10
X											

4. At the end of the session, please make “X” below on the patient’s immediate responses for today’s treatment:

	Question Items	Yes	No	Unknown
a	Did the patient appear to be relaxed?			
b	Was the patient dozed off during the treatment?			
c	Did the patient still feel the “tapping” sensation at the end of the session?			
d	Was the pulse/heart rate of the patient slower than the beginning of the session?			
e	Has the patient’s skin temperature of hands noticeably changed (either warmed up or cooled down)?			
	Other observations?			

5. Did the patient report any adverse event per CTCAE v4.0 at this visit? Please make a circle below:

NO YES, If “YES” is answered, please describe the details here:

Adverse Event	Start Date	Stop Date	Grade (1-5) Mild, Moderate, Severe, Life Threatening, Fatal	Attribution	Comments
Skin bruise					
Hematoma					
Skin infection					
Presyncope					
Syncope					
Nausea					

6. Was today's session completely followed the study protocol requirement?

Question Item	YES	NO	If "no", please explain here
Was today's session completely followed the study protocol requirement?			

Signature of acupuncturist

Name of acupuncturist

11/8/2019

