In weeks 10 to 20, the two study groups switched treatments. Participants who received no acupuncture for the first 10 weeks then received acupuncture once per week for 10 weeks. This was called the “delayed acupuncture” group. Participants who received acupuncture for the first 10 weeks did not receive acupuncture between weeks 10 and 20.

Three surveys were used to find out if acupuncture had an effect:

- the Endocrine Symptom Subscale (ESS) was used to assess hormonal symptoms,
- the Hot Flash Score (HFS) was used to measure the number and severity of hot flashes,
- The FACT-B measured disease-specific quality of life in patients with breast cancer.

4. What Were The Results?

Overall, this study found significant decreases in hot flashes and hormonal symptoms after 10 weeks of acupuncture given 2 times per week.

When a result is significant, it means the result was unlikely to have happened by chance.

At week 10, more participants in the acupuncture group (64%) had improvements in the number and severity of hot flashes, compared with the control group (18%).

Also, more participants (54%) experienced a general improvement in all hormonal symptoms in the acupuncture group vs the control group (26%).

The study also found that breast cancer-specific quality of life was significantly improved at week 10 in the acupuncture group.

Participants in the delayed acupuncture group (who started acupuncture at week 10 and received 10 weekly sessions) also reported significant improvements in hormonal symptoms from week 10 to week 20.

Overall, these findings show that many participants felt acupuncture decreased the number and severity of hot flashes, and improved their quality of life.

5. What Were The Side Effects?

There were no acupuncture-related side effects reported by participants.

6. How Has This Trial Helped?

This study found that acupuncture could help reduce the side effects of hormonal medications, which might help patients keep taking them.

Future research could look at whether improving hot flashes and other hormonal symptoms leads to more people completing cancer treatment and whether it ultimately improves cancer-related outcomes in women with breast cancer.

8. Where Can I Learn More About This Trial?

You can find more information about this trial at the links below:

- On www.clinicaltrials.gov: NCT03783546
- In the following publication(s):
 - o <https://pubmed.ncbi.nlm.nih.gov/35998768/>

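### Sections 7.8, 8.3 and 8.4 word the session-level adverse event enquiry as acupuncture-related, while 9.1.1, 9.2, 9.6 and the treatment form call for any adverse event, with attribution graded afterwards

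*Combined protocol and SAP*

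**What the plan says.** Three sections describe what happens at an acupuncture session, and each attaches a relatedness qualifier.

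- Section 8.4, on the enquiry: "Individuals receiving acupuncture will be asked about acupuncture-related adverse events at each acupuncture treatment". The telephone line offered in the same section is likewise for potential acupuncture-related events.
- Section 8.3, on collection: "Any side effects related to the acupuncture will be collected by treating acupuncturists".
- Section 7.8, on the content of the Acupuncture Treatment Form, lists "patient immediate responses, and any acupuncture-related adverse events".

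Other parts of the same protocol set a wider rule.

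- Section 9.1.1 counts an adverse event "even if the event is not considered to be related to the study".
- Section 9.2 has participating investigators assess adverse events at all evaluation time points and has every event recorded, whatever its source. Section 9.6 also covers all adverse events, serious or not.
- Item 5 of the form itself (Appendix VI) reads: "Did the patient report any adverse event per CTCAE v4.0 at this visit". It has columns for grade and attribution.
- Causality is rated after an event is reported. Section 8.4 continues: "Any reported events will be evaluated for the likelihood that they occurred as a result of acupuncture". The five-level scale in 9.1.3.3 ends with "Unrelated - The AE is clearly NOT related to the study treatment".

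**The concern.** Asking a participant about acupuncture-related events is a different question from asking what has changed since the last visit. The first asks her to make a causal judgement before she answers. Bruising at a needle site passes that test easily. Dizziness later the same day, or a bad night, may not, and she may not mention it.

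An event that is not mentioned is not graded or attributed. It also cannot be considered under 9.4.1, which brings Grade 2 and 3 events into expedited reporting only when they are unexpected and at least possibly related. What is at stake is how complete the non-serious adverse event record is, and how much reassurance a statement about treatment-related side effects can carry.

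**Working it through.** The protocol gives no event rate or safety sample size calculation on this point, so there is no planned figure to reproduce. The check is a comparison of texts and a count of the sessions affected.

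**1. What is asked.** Section 8.4 limits the question to related events. It does not say who asks; the acupuncturist's part comes from 7.8, where the treating acupuncturist completes the form, and from 8.3. Sections 9.1.1 and 9.2 contain no such limit. Staff who follow 8.4 literally do not put the question that 9.1.1 implies.

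**2. What is recorded.** Section 7.8 describes the form as documenting related events. The form in Appendix VI asks about any event under CTCAE v4.0. The description is therefore narrower than the instrument. The form's named rows (bruise, hematoma, skin infection, presyncope, syncope, nausea) lean towards effects of needling, but item 5 is not restricted to them.

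**3. Whether the form repairs the question.** Item 5 records whether the patient reported an event. What she reports depends partly on what she was asked, and 8.4 sets that. An unrestricted form following a restricted question can still be incomplete.

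**4. Whether another scheduled enquiry repairs it.** Table 1 places NCI-CTCAE only at acupuncture sessions, 20 or 10 according to arm. It shows no CTCAE item at baseline or tied to the week 10 and week 20 assessments. Section 9.2 requires investigators to assess events at all evaluation time points but specifies no question or form for doing so. The scheduled route is therefore the one that 7.8, 8.3 and 8.4 narrow.

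**5. What happens to the scale.** The scales in 8.4 and 9.1.3.3 have two lower levels, doubtfully related and unrelated. Under an open question these hold the events that turn out to have another cause. Under a related-events question they are likely to be under-filled.

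**6. Reach.** With 40 participants randomized per arm (section 10.1) and full attendance:

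- immediate arm: 40 × 20 = 800 sessions
- delayed arm: 40 × 10 = 400 sessions
- total: 800 + 400 = 1,200 planned enquiries

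This counts occasions on which the question is put. It is not an estimate of missed events, for which the documents give no basis.

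**The case against.** The strongest reply is that this is a drafting inconsistency inside a protocol whose governing rules are sound. None of 7.8, 8.3 or 8.4 says that other events are to be ignored. Sections 9.2, 9.4.2 and 9.6 cover adverse events without a relatedness limit, the form in use is unrestricted, and 8.4 rates causality after reporting. This stands, and it rules out several stronger readings that a reader might infer.

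- *That causality is settled before anything is collected, or that the lower attribution levels must be empty.* Section 8.4 itself provides for reported events that prove unrelated, and 9.2 admits events from any source. Under-filled is as far as the text goes.
- *That the 9.4.1 rule can act only on events the acupuncturist has already accepted as related.* Section 9.2 gives investigators their own assessment, and no section names the person who assigns attribution. Section 9.4.1 also covers all serious adverse events, which 9.1.2 defines regardless of causality; Grade 4 events unless expected and listed as exempt; and Grade 5 events during participation or within 30 days of the last intervention.
- *That the statement in the plain language summary (Appendix XVI), "There were no acupuncture-related side effects reported by participants", can be turned into an upper limit on the event rate and then inflated for filtering.* The summary's 158 participants come from three countries and two protocol numbers. The collection procedures for those outside this protocol are not shown, the number who received acupuncture is not given, and any filtering share would be invented.

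It can also be said that FACT-B and FACT-ES ask about arm swelling and dizziness, and that sleep is measured in several ways. These are outcome instruments at fixed weeks, and no section routes their answers into adverse event reporting. They soften the concern without removing it.

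The reply does not answer points 3 and 4 of the check. The wider rules say what must be recorded once known, but the only scheduled enquiry is the one described in narrower terms.

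**Conclusion.** The point holds as an internal conflict with a likely effect on ascertainment. Sections 7.8, 8.3 and 8.4 cannot be followed literally together with 9.1.1, 9.2, 9.6 and item 5 of the form. Where staff follow 8.4, events without an obvious link to needling are likely to be under-elicited, so fewer reach attribution or the Grade 2 and 3 rule in 9.4.1.

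The wording reaches every planned session, up to 1,200, but the loss of events cannot be sized from the documents. The conclusion assumes that the question was put as 8.4 words it; if staff asked openly, as item 5 suggests, little would be lost. It does not support a claim that collection across the protocol is confined to related events, or that serious events escape reporting.

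**What to change.** Reword 7.8, 8.3 and 8.4 to one rule, in line with 9.1.1, 9.2 and item 5 of the form:

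- at each session the participant is asked about any new or worsened sign, symptom or condition since the last visit;
- every such event is recorded on the Acupuncture Treatment Form;
- attribution on the 9.1.3.3 scale is assigned after the event is recorded.

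Naming an investigator who did not treat the participant to assign attribution would be a reasonable addition. No section requires it, and the study PI is also the lead acupuncturist (section 8.3), so it is optional.

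The cost is edits to three sections, a short scripted question and more minor unrelated events to enter.

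If collection is complete, as the existence of a results summary suggests, rewording recovers nothing. In that case, state beside the safety conclusion which question was actually asked at sessions.
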